7.2 Randomization, Stratification and Blinding

Study treatment will consist of FDY-5301 or placebo.

All subjects who fulfill all study eligibility criteria will be randomized to receive one of the treatment kits allocated by a computer-generated randomization code (FDY-5301 at 1 mg/kg, or 2 mg/kg, or volume-matched placebo). Randomization will be stratified by whether the subject has pelvic or lower limb fractures.

The clinical trial site will remain blinded to treatment allocation of active or placebo, as placebo and active vials will be identical in appearance.

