10 STATISTICS

A separate Statistical Analysis Plan (SAP) will provide additional details for statistical analyses and data displays.

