10.2.4.1 Primary Efficacy Analyses

There are two co-primary efficacy endpoints defined in this study:

- CPAx total score at Day 10 (or at hospital discharge, whichever occurs first)
- Organ dysfunction total TTR until Day 28

Both primary endpoints will be compared across treatment groups and tested at the 0.05 level of significance and, by convention, both endpoints must demonstrate statistical significance (i.e., $p \le 0.05$) to conclude treatment superiority for regulatory purposes.

For the first primary efficacy endpoint, CPAx total score at Day 10 (or at hospital discharge, whichever occurs first), the following hypothesis will be tested:

$$H_0$$
: $\mu_{Tp} = \mu_p \ v. s. H_a$: $\mu_{Tp} \neq \mu_p$

Where μ_{Tp} , μ_p denote the CPAx total score at Day 10 (or at hospital discharge, whichever occurs first) in the pooled treatment group (FDY-5301 1 mg/kg and FDY-5301 2 mg/kg combined) and placebo groups, respectively. As the primary analysis, the treatment comparison of the CPAx total scores will be performed using analysis of covariance (ANCOVA). The model will include CPAx total score at Day 10 (or at hospital discharge, whichever occurs first) as dependent variable treatment and stratification category (with or without presence of pelvic or lower limb fractures) as factors; and "baseline" CPAx (the first available datapoint) as a continuous covariate.

The p-values, least-squares means, standard errors, and the 2-tailed 95% confidence intervals for the treatment groups and placebo group will be presented.

Confidential Page 47 of 64

If the difference between the means of the pooled treatment group compared to the placebo group is statistically significant, a step-down procedure will be followed to test the individual FDY-5301 doses compared to placebo. The following testing order of doses will be used:

- 1) FDY-5301 2 mg/kg versus placebo
- 2) FDY-5301 1 mg/kg versus placebo

The same statistical method as for the comparison between the pooled treatment group and placebo will be used.

For the second primary efficacy endpoint, organ dysfunction total TTR, the time will be calculated as date of recovery minus date of treatment start plus 1 day. The time to recovery will be estimated using Kaplan-Meier methodology. The Kaplan-Meier curves will be plotted and the time to recovery will be compared using log-rank test at significance level 0.05. The pooled versus placebo and then step-down analysis procedure will be used.

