10.2.4.2 Secondary Efficacy Analysis

For secondary endpoints, a sequential analysis will be performed. The continuous secondary efficacy endpoints of MRC-SS and worst SOFA score will be analyzed with an ANCOVA model similar to the one described for the primary endpoint of CPAx total score. The secondary endpoint of overall survival at Day 28 will be analyzed using a Kaplan-Meier approach and a log-rank test, similar to the methodology described for the primary endpoint of organ dysfunction total TTR until Day 28.

The pooled treatment groups versus placebo will be analyzed first, followed by a step-down analysis.

The p-values, least-squares means, standard errors, and the 2-tailed 95% confidence intervals for the treatment groups and placebo group will be presented, where appropriate.

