10.2.4.4 Subgroup Analyses

To assess the heterogeneity of treatment effects among subgroups, the primary and secondary endpoints will be summarized descriptively and analyzed by stratification group (with or without presence of pelvic or lower limb fractures).

In addition, forest plots displaying effect estimates and 95% CIs for subgroups and the entire ITT population will be provided for the primary and secondary endpoints.

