APPENDIX 4: ORGAN DYSFUNCTION TTR

Time to recovery (TTR) is defined as the first day of meeting the criteria for organ failure recovery in all systems listed below, without any subsequent days with further organ system failure.

Cardiovascular recovery

Mean arterial pressure >60 mmHg and no inotropic/vasopressor support (dopamine, dobutamine, epinephrine, norepinephrine, phenylephrine, or vasopressin)

Hematologic recovery

Platelet count >120,000/mL

Hepatic recovery

Serum bilirubin <3 mg/dL

Renal recovery

No dialysis and creatinine <1.3 mg/dL

Respiratory recovery

No mechanical ventilation or PaO₂/FiO₂ >300

FiO2 = fraction of inspired oxygen; PaO2 = partial pressure of arterial oxygen.

Source: Raymond SL, Hawkins RB, Wang Z, et al. Prospective Validation of a Transcriptomic Metric in Severe Trauma. Ann Surg. 2019 Jan 24. doi: 10.1097/SLA.0000000000003204. (Epub ahead of print)

Confidential Page 61 of 64

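### The log-rank test for organ dysfunction TTR, a co-primary endpoint, does not name the fracture stratum used in randomisation and in the CPAx model

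*Combined protocol and SAP*

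**What the plan says.** Section 7.2 states: "Randomization will be stratified by whether the subject has pelvic or lower limb fractures". Section 1.4 gives the purpose as equal representation of the strata across groups. In Section 10.2.4.1 the CPAx ANCOVA has treatment and "stratification category (with or without presence of pelvic or lower limb fractures) as factors", plus baseline CPAx as a covariate.

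For TTR the same section gives Kaplan-Meier estimation and then: "the time to recovery will be compared using log-rank test at significance level 0.05". The pooled comparison comes first, followed by the dose step-down. The synopsis and the power statement in Section 10.2.7 also say log-rank without strata.

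In Section 10.2.4.2, "worst SOFA score will be analyzed with an ANCOVA model similar to the one described for the primary endpoint of CPAx total score", while "overall survival at Day 28 will be analyzed using a Kaplan-Meier approach and a log-rank test", on the TTR pattern. Section 10.2.4.4 analyses the primary and secondary endpoints by fracture group and promises "forest plots displaying effect estimates and 95% CIs for subgroups and the entire ITT population". Section 10 adds: "A separate Statistical Analysis Plan (SAP) will provide additional details for statistical analyses and data displays". The supplied text contains no such separate plan.

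**The concern.** A stratified design is normally analysed with its stratification factor. The plan does this explicitly for CPAx and, through the similar-model wording, for MRC-SS and worst SOFA. It does not do so for TTR and gives no reason.

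The contrast with SOFA is the sharpest. Appendix 4 says: "Time to recovery (TTR) is defined as the first day of meeting the criteria for organ failure recovery in all systems listed below". Those five systems (cardiovascular, hematologic, hepatic, renal, respiratory) correspond to five of the six SOFA domains in Section 6.1.4. A secondary endpoint built on largely the same organs would therefore be adjusted for fracture, while the co-primary endpoint would not.

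Three things are at stake:

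- **Power.** Both co-primaries must reach significance, and TTR has the lower stated power.
- **Pre-specification.** Silence leaves two defensible p-values for one co-primary test.
- **Estimation.** Forest plots need a between-group effect estimate. Kaplan-Meier curves and a log-rank p-value do not supply one, and none is named for TTR.

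**Working it through.** **Inputs from Section 10.2.7:** 252 randomised 1:1:1, 213 evaluable after 15% drop-out (71 placebo, 142 pooled active), median TTR 7 vs 4.9 days (ratio 4.9/7 = 0.70), two-sided 0.05, 213 events.

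**The plan's own figures.** The Schoenfeld formula with a placebo share of 1/3 gives

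Φ(√(213 × 1/3 × 2/3) × |ln 0.70| − 1.96) = Φ(6.880 × 0.3567 − 1.96) = Φ(0.494) = 68.9%,

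which agrees with the stated 70% or so. For CPAx, a two-sample t-test with 142 vs 71, difference 6 and SD 12 gives 92.8%, which agrees with the stated >90%. The formula has no term for strata, so the comparison below needs simulation.

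**Simulation assumptions not in the documents.**

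- Exponential recovery times within stratum, rounded up to whole days and censored at Day 28.
- Overall placebo median held at 7 days.
- Recovery hazard ratio 1/0.7 for both doses within each stratum.
- Blocks of 6 within stratum.
- Half of subjects in each stratum, or 30% in the faster-recovering one.
- Stratum hazard ratio for recovery from 1 to 2.
- No deaths.

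Each setting has 40,000 runs (Monte Carlo SE at most 0.25 point for each power).

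Power (%), without / with the stratum, 213 subjects, half in each stratum:

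| Stratum HR | Pooled vs placebo | 2 mg/kg vs placebo |
|---|---|---|
| 1 | 66.4 / 65.9 | 54.6 / 53.9 |
| 1.25 | 65.4 / 65.6 | 53.6 / 53.7 |
| 1.5 | 63.5 / 65.8 | 51.4 / 53.3 |
| 2 | 58.0 / 64.8 | 46.5 / 53.1 |

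Change in power from stratifying (points), over 213 or 252 subjects and a 50% or 30% share:

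| Stratum HR | Pooled | 2 mg/kg step-down |
|---|---|---|
| 1 | −0.5 to −0.3 | −0.8 to −0.5 |
| 1.25 | 0.0 to +0.4 | 0.0 to +0.2 |
| 1.5 | +1.4 to +2.2 | +1.1 to +1.9 |
| 2 | +4.3 to +6.8 | +4.3 to +6.6 |

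At HR 1 the simulated power is below 68.9% partly because not everyone recovers by Day 28. The exponential assumption leaves 0.5^(28/7) = 6.25% of placebo and 0.5^(28/4.9) = 1.9% of active subjects unrecovered. Events are then 71 × 0.9375 + 142 × 0.981 ≈ 206, for a formula power of 67.5%.

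**Sensitivity.** A second simulation used continuous times, exact balance of strata across arms and a fracture share of 30 to 70%. Gains were about 1 to 3 points at a fracture hazard ratio of 0.67 and 3 to 8 points at 0.5; at HR 1 the cost was at most 1 point.

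**Type I error** (213 subjects, no treatment effect). At a stratum HR of 2, or equivalently 0.5, the test without the stratum rejects in about 3.7 to 4.5% of trials, and the stratified test in about 5%. At HR 1 both are near 5%.

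**Disagreement.** Under the planned effect the two tests reach different conclusions at 0.05 in about 3% of trials at HR 1, 5 to 6% at HR 1.5 and 10% at HR 2 (213 subjects, half in each stratum).

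**The case against.** The strongest reply is that no error has been shown. The test is valid as written, the stated power reproduces, and Section 10 leaves details to a separate SAP, where a stratified test and a forest-plot estimate could well be specified. All of that stands and limits the point to the protocol text.

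Different handling of the endpoints can also be defended. Pelvic or leg fracture plausibly bears directly on CPAx items such as standing, transfers and stepping. Nothing in the documents says it predicts blood pressure, platelets, bilirubin, creatinine or ventilation. This too stands. Only the HR 2 case gives a sizeable gain, and with equal strata it implies median recovery of about 5.0 and 10.1 days, for which the documents offer no support. At HR 1.25 there is no material difference. The stratum is also only implied for worst SOFA, because a similar model need not be an identical one.

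Two parts of the reply do not carry. The subgroup analysis in Section 10.2.4.4 reports results within each stratum but does not adjust the primary test. And uncertainty about prognosis does not favour silence: the cost of stratifying is about half a point of pooled power, while the possible gain is several points and the choice of test is closed before unblinding.

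**Conclusion.** The point holds as an omission worth correcting, not as an error that invalidates the analysis. The protocol does not say whether the TTR log-rank test uses the randomisation stratum, and it names no between-group effect estimate for TTR. The second gap does not depend on whether fracture is prognostic.

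The effect on power ranges from a small loss through no material change at a stratum HR of 1.25 to a gain of several points at HR 2. Where a given trial falls depends on the prognostic strength and prevalence of fracture, neither of which the documents state. Type I error is not inflated either way. All figures ignore deaths, and none is offered for Day 28 survival because no mortality rate is given. Confidence is moderate, mainly because the separate SAP is not available.

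**What to change.** In Section 10.2.4.1 and the synopsis, specify for TTR a log-rank test stratified by pelvic or lower limb fracture as randomised, for the pooled comparison and for both step-down dose comparisons. Name a Cox hazard ratio for recovery with 95% CI as the effect estimate. For the forest plots in Section 10.2.4.4, stratify it by the same factor in the overall ITT row and leave it unstratified within each fracture subgroup. Use the same method for Day 28 survival, for consistency only. If the separate SAP already says this, align the protocol text with it.

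The cost is wording: no new data or subjects, and only two strata. The downside is about half a point of pooled TTR power, and 0.5 to 0.8 point for the 2 mg/kg step-down, if fracture turns out not to be prognostic.

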10.2.4.2 Secondary Efficacy Analysis

For secondary endpoints, a sequential analysis will be performed. The continuous secondary efficacy endpoints of MRC-SS and worst SOFA score will be analyzed with an ANCOVA model similar to the one described for the primary endpoint of CPAx total score. The secondary endpoint of overall survival at Day 28 will be analyzed using a Kaplan-Meier approach and a log-rank test, similar to the methodology described for the primary endpoint of organ dysfunction total TTR until Day 28.

The pooled treatment groups versus placebo will be analyzed first, followed by a step-down analysis.

The p-values, least-squares means, standard errors, and the 2-tailed 95% confidence intervals for the treatment groups and placebo group will be presented, where appropriate.

10.2.4.3 Exploratory Efficacy Analyses

Continuous variables will be summarized by descriptive statistics (n, mean, median, standard deviation, minimum, and maximum) by treatment group. Continuous variables will also be analyzed using analysis of covariance or analysis of variance. The least-squares means, standard errors, and the 2-tailed 95% confidence intervals for the treatment group and placebo group will be presented.

Categorical variables will be summarized by frequency and percentage by treatment groups. Categorical variables will be analyzed using a Pearson's Chi-square test or Cochran-Mantel-Haenszel test.

Time to event data will be analyzed using Kaplan-Meier lifetables and a log-rank test to compare time to efficacy between treatment groups and placebo groups.

Confidential Page 48 of 64

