2 TRIAL OBJECTIVES AND ENDPOINTS

The purpose of the trial is to evaluate the efficacy, safety, and PK of FDY-5301 compared to placebo in major trauma ICU patients at risk of ICUAW.

Objectives	Endpoints								
Primary	Coprimary								
To assess the effect of FDY-5301 on muscle function and organ dysfunction in the major trauma ICU population	 Chelsea Critical Care Physical Assessment Tool (CPAx) total score at Day 10, or hospital discharge, whichever occurs first Organ dysfunction total time to recovery (TTR) until Day 28 								
Secondary	Secondary								
To assess the effects of FDY-5301 on other clinical outcomes in the major trauma ICU population	The secondary endpoints will be analyzed in the following sequence: • Medical Research Council Sum Score (MRC-SS) at Day 28 or hospital discharge, whichever occurs first • Worst Sequential Organ Failure Assessment (SOFA) score during ICU stay • Overall Survival at Day 28								
Safety	Safety								
To investigate the safety and tolerability of up to 7 daily bolus IV doses of FDY-5301 in the major trauma ICU population	Safety will be evaluated based on occurrence of or changes throughout the study in the following parameters: • Adverse events (AEs), treatment-emergent adverse events (TEAEs) and serious adverse events (SAEs) • Clinical laboratory assessments (hematology, clinical chemistry, and thyroid function tests) • 12-lead electrocardiogram (ECG) assessments								
Exploratory	Exploratory								
To assess the effects of FDY-5301 on skeletal muscle, muscle function, and other clinical outcomes and to investigate the PK of up to 7 daily bolus IV doses in the major trauma ICU population	 Overall survival at Month 3 and Month 6 from date of injury Time to successful ventilator extubation from time of first dose Time to hospital discharge from first hospital arrival time and time of first dose, and discharge disposition (e.g., home, home with community support, rehabilitation unit, or nursing home) 								

Confidential Page 22 of 64

- Incidence of sepsis through Day 28
- SOFA score and sub score components at Days 1, 3, 7, 14, 21, and Day 28 or ICU discharge, whichever occurs first
- CPAx total score and sub score components at Days 1, 3, 7, 10 (sub score components only), 14, 21, and Day 28 or hospital discharge, whichever occurs first

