6.1.9 Time of Extubation

Time of intubation(s) and successful extubation(s) will be recorded. Extubation will be considered successful if subject remains extubated for at least 24 hours.

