6.1.11 Discharge and Disposition

Time of hospital discharge and disposition type (e.g., step-down unit, rehabilitation facility, home) will be recorded. Time of hospital discharge will be defined as the date the subject is cleared for discharge from the hospital.

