10.2.2 Handling of Missing Data

CPAx total scores will be analyzed using ANCOVA on observed data. To assess the impact of missing data, multiple imputation will used as supplementary analysis. Tipping-point analysis will also be performed. Details will be described in the SAP.

For organ dysfunction total TTR, no imputation will be performed. For all other endpoints, missing observations will be excluded from analysis.

Descriptive summaries of efficacy and safety measures will be based on observed data.

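### Exploratory time to hospital discharge and time to extubation are assigned Kaplan-Meier and log-rank with no rule for deaths before the event

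*Combined protocol and SAP*

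**What the plan says.** Section 10.2.4.3 (Exploratory Efficacy Analyses) states: "Time to event data will be analyzed using Kaplan-Meier lifetables and a log-rank test". Section 2 lists two exploratory endpoints that fall under this rule: "Time to successful ventilator extubation from time of first dose" and "Time to hospital discharge from first hospital arrival time and time of first dose".

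The event definitions do not mention death. Section 6.1.9 says "Extubation will be considered successful if subject remains extubated for at least 24 hours". Section 6.1.11 says "Time of hospital discharge will be defined as the date the subject is cleared for discharge from the hospital".

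The only missing-data rule that reaches these endpoints is in Section 10.2.2: "For all other endpoints, missing observations will be excluded from analysis". It does not say whether a death counts as a missing observation. Section 10 leaves further detail to a separate SAP. The combined document contains no censoring, competing-event or worst-outcome rule for these two endpoints.

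Mortality has its own analyses. Section 10.2.4.2 says "The secondary endpoint of overall survival at Day 28 will be analyzed using a Kaplan-Meier approach and a log-rank test", and Section 2 adds, as exploratory, "Overall survival at Month 3 and Month 6 from date of injury".

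**The concern.** A subject who dies in hospital can never be discharged alive, and one who dies on the ventilator can never be extubated. Death is therefore a competing event for both endpoints. Deaths are foreseeable here: entry requires hemorrhagic shock and ICU admission with anticipated ventilation, and the plan itself makes survival an endpoint.

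Naming Kaplan-Meier without a death rule leaves the coding open, and the coding changes what is estimated:

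- **Censored at death.** The estimator treats the subject as someone who would still have gone home or been extubated at the same rate as the survivors. 1-KM then exceeds the proportion who have the event alive.
- **Excluded as missing** (a possible reading of Section 10.2.2). The result is conditional on not dying before the event, and the proportion is again too high.
- **Kept event-free in the risk set to a fixed horizon.** 1-KM equals the cumulative incidence and the problem disappears.

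What is at stake is how two clinically readable exploratory results are interpreted: the proportion off the ventilator and the proportion out of hospital. Under the first coding, an arm with more early deaths would look no worse on either.

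**Working it through.** **The plan's own time-to-event figure.** The only one is the power for organ dysfunction TTR in Section 10.2.7 (213 events, medians 7 and 4.9 days, 1:1:1 allocation with active pooled). By the Schoenfeld formula, √(213 × 1/3 × 2/3) × |ln 0.7| = 6.880 × 0.3567 = 2.454, and Φ(2.454 − 1.960) = 68.9%. This agrees with the stated value of about 70%. No corresponding figure exists for discharge or extubation.

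**Inputs.** Arm sizes are 84 placebo and 168 pooled active (Section 10.2.7). All other inputs are assumptions: median time to event 18 days for discharge and 6 days for extubation; deaths front-loaded (Weibull cumulative hazard c·t^0.7); mortality before the event by Day 28 of 5%, 10% or 20%. Day 28 is used here only for illustration.

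**Formulas.** With λ = ln 2 / median:

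- 1-KM with deaths censored = 1 − exp(−28λ)
- cumulative incidence of the event alive = ∫₀²⁸ λ·exp(−λt − c·t^0.7) dt, with c solved to give the assumed mortality
- standard error = √(CIF(1 − CIF)/n)

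For discharge, λ = 0.0385 and 1-KM = 66.0%. For extubation, λ = 0.1155 and 1-KM = 96.1%.

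| Mortality before event | Discharge: 1-KM vs true | Excess | Extubation: 1-KM vs true | Excess |
|---|---|---|---|---|
| 5% | 66.0% vs 63.5% | 2.5 | 96.1% vs 91.5% | 4.5 |
| 10% | 66.0% vs 61.0% | 5.0 | 96.1% vs 87.0% | 9.0 |
| 20% | 66.0% vs 55.8% | 10.2 | 96.1% vs 77.8% | 18.2 |

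The excess is in percentage points and is computed before rounding. At 10%, the discharge excess is 1.3 standard errors in the pooled arm and 0.9 in placebo; the extubation excess is 3.5 and 2.5.

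Excluding deaths instead gives, at 10%, 61.0/0.90 = 67.7% for discharge and 87.0/0.90 = 96.7% for extubation.

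**Check with constant hazards.** Here CIF = λ/(λ+μ) × [1 − exp(−28(λ+μ))]. For a median of 14 days and 10% mortality, λ = 0.0495 and μ = 0.0071, so CIF = 0.874 × 0.795 = 69.5%, against 1-KM of 75.0% (excess 5.5 points). Across medians of 7 to 20 days and mortality of 5% to 30%, the excess runs from about 2 to 26 points.

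**Between-arm comparison.** Assume equal event hazards in both arms and mortality before the event of 10% on placebo and 20% on active (84 vs 168 subjects, 4,000 simulated trials, Day 28 horizon).

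| | Median 14 days | Median 7 days |
|---|---|---|
| 1-KM, both arms | 75.0% | 93.8% |
| True proportion alive with event, placebo vs active | 69.5% vs 63.8% | 85.5% vs 77.0% |
| Log-rank against active, deaths censored | 2.7% | 2.8% |
| Log-rank against active, deaths kept to Day 28 | 11.9% | 21.1% |

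With deaths censored, the test rejects at its nominal one-tail rate: it does not respond to the extra deaths.

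**The separate survival test.** For 10% vs 20% mortality by Day 28, expected deaths are 84 × 0.10 + 168 × 0.20 = 42. The hazard ratio is ln 0.80/ln 0.90 = 2.12. The Schoenfeld power is Φ(√(42 × 2/9) × ln 2.12 − 1.96) = Φ(2.29 − 1.96), about 63%.

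**The case against.** The strongest reply is that the plan names a method and is merely silent on one coding rule. Nothing in it says that deaths will be censored, and Kaplan-Meier with deaths held event-free to a horizon is still Kaplan-Meier. That stands: the defect is an unstated rule, and the bias arises only under some codings.

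A log-rank test with deaths censored is also a valid test of the event rate among those still alive and at risk. With equal event hazards, finding no difference is the right answer to that question. This too stands. The bias lies in reading 1-KM as a proportion, and in taking the test as a comparison of proportions with the event alive.

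Two stronger readings are tempting, and the documents do not support them:

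- A reader might infer that the plan hides a mortality harm. It does not. Survival is analysed at Day 28, Month 3 and Month 6. In the example above, the Day 28 survival test (about 63% power) is far more sensitive than either exploratory comparison, even after the fix. Its limits are that it comes last in the secondary sequence and that its power falls to about 22% for 10% vs 15%.
- A reader might infer that deaths would be counted as early discharges and create a false benefit. In simulation, with death hazards of 0.006 and 0.013 per day and a median discharge of 18 days, that coding gives a mean z of about +0.95 in favour of active. But Section 6.1.11 ties discharge to clearance to leave, and Section 6.1.9 requires 24 hours off the tube. On an ordinary reading, a death meets neither.

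Finally, the sizes depend on assumptions. Deaths after successful extubation do not compete with extubation, so 10% total mortality would give a smaller bias than 10% before the event.

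**Conclusion.** The point holds as a minor one. Section 10.2.4.3 applies Kaplan-Meier and log-rank to two endpoints that death precludes, without saying how deaths count. If deaths are censored, the reported proportions discharged or extubated alive are too high: about 2.5 to 10 points for discharge and 4.5 to 18 points for extubation at 5% to 20% mortality before the event, given assumed medians of 18 and 6 days. The direction is certain under that coding. The size cannot be taken from the documents, which give no mortality, length of stay or ventilation time.

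Under the same coding, these two comparisons would not reflect a mortality difference, which is left to the separate survival analyses. Both endpoints are exploratory, and the coprimary conclusions are not affected by this point.

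**What to change.** For these two endpoints, add to Section 10.2.4.3 or the SAP:

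- Report the Aalen-Johansen cumulative incidence of discharge alive and of extubation alive, with death as a competing event, in place of 1-KM.
- Compare arms with Gray's test, or keep deaths event-free in the risk set to a stated horizon in the log-rank test.
- Match the horizon to data collection for each endpoint. In Table 1, extubation is recorded to Day 28, while discharge and disposition are also recorded at Months 3 and 6. Day 28 therefore suits extubation; discharge needs its own stated horizon.
- Report deaths before the event by arm next to each result.
- If a log-rank test with deaths censored is kept, label it as a cause-specific comparison.

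The cost is a few sentences and standard software options. Survival, discharge and extubation are already collected. The downside is that the reported proportions become slightly less favourable.
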